3. INTRODUCTION

GSK2881078 belongs to a novel class of non-steroidal, Selective Androgen Receptor Modulators (SARMs) and is under investigation by GlaxoSmithKline (GSK) for treatment of impaired mobility, disability and functional limitation in older men and post-menopausal women with muscle weakness associated with Chronic Obstructive Pulmonary Disease (COPD). Conditions such as COPD, congestive heart failure, and chronic kidney disease can demonstrate significant muscle wasting and associated functional impairment, especially in advanced states. Physical therapy and exercise have been shown in these conditions to increase muscle mass and improve physical function. The use of the natural steroid androgen receptor agonist, testosterone, has also been shown in these conditions to induce similar benefits, but such use is limited by prostate effects and androgenic effects. A non-steroidal, selective androgen receptor agonist can potentially act positively on muscle and bone while not adversely affecting the prostate gland in men, or inducing hirsutism or virilization in women.

3.1. Study Rationale

This study is the third clinical study with administration of GSK2881078 in humans, and it will be the first administration to the target population, defined as older men and post-menopausal female participants (50-75 years of age) with COPD and muscle weakness, participating in home exercise. This study will evaluate the safety and tolerability over 13 weeks of dosing in this population. This study will also evaluate the anabolic effects of GSK2881078 as measured by changes from baseline in leg strength, muscle mass, and functional measures.

3.2. Background

Impaired physical function and muscle dysfunction are a major consequence of COPD and may be associated with increased mortality, poor quality of life, and increased health care use. Physical therapy and exercise have been shown to increase muscle mass and improve physical function in participants with COPD [Maltais, 2014]. Increased muscle mass and improved physical function have also been shown with the natural steroid androgen receptor agonist testosterone in participants with COPD [Atlantis, 2013]. However, use of testosterone to treat muscle dysfunction in participants with COPD may be limited due to adverse effects in both men and women. A non-steroidal, selective androgen receptor agonist can potentially act positively on muscle while avoiding unwanted effects seen with testosterone (e.g., prostate hypertrophy in men or hirsutism or virilization in women). Currently, there are no medications approved by the United States Food and Drug Administration (FDA) for the treatment of muscle wasting disorders of any aetiology.

The scientific opportunity for the treatment of muscle-wasting and associated disorders is presented through the development of non-steroidal molecules that act via the androgen receptor in a cofactor/cellular/tissue-selective manner. SARMs bind to the androgen receptor inducing a unique receptor conformation which allows only certain co-activator and co-repressor proteins to interact. These unique receptor-cofactor ensembles confer differential regulation of target genes and other receptor-mediated pathways. The

differential activity allows SARMs to function as potent androgens in target tissues such as muscle and bone, but function as antagonists, or partial agonists, in other tissues or organs such as the prostate or skin. Further, an appropriately selective SARM could be given to post-menopausal women without inducing hirsutism or virilization, which occurs with steroid androgen receptor modulators.

While no SARM has been approved for clinical use, there is growing clinical experience with this class of compounds. Enobosarm has been through a series of clinical studies and recently finished a Phase 3 program evaluating the efficacy for treatment of muscle loss and functional impairment in cancer cachexia [Dalton, 2011; Dobs, 2013]. Although the phase 3 study for Enobosarm did not show an improvement in stair climb power (co-primary endpoint), there appeared to be a consistent effect of enobosarm on muscle mass and strength in study participants in phase 2 trials. An additional SARM, LGD-4033, has shown no apparent safety signals and has demonstrated an increase in lean body mass (LBM) in repeat dosing in healthy male volunteers [Basaria, 2012]. GSK also has clinical experience with SARM compounds, GSK971086 and GSK2849466. These compounds were evaluated in first-time-in-human studies in healthy male volunteers, both showing expected effects on biomarkers and no safety signals in studies less than 3 weeks. However, both of these compounds were discontinued because of unexpected toxicity observed in longer preclinical safety studies.

A detailed description of the chemistry, pharmacology, efficacy, and safety of GSK2881078 is provided in the Investigator's Brochure (IB).

3.3. Benefit/Risk Assessment

More detailed information about the known and expected benefits and risks and reasonably expected AEs of GSK2881078 may be found in the IB.

3.3.1. Risk Assessment

Potential Risk of Clinical Significance	Summary of Data/Rationale for Risk	Mitigation Strategy
Investigational Product (IP) GSK2881078		

Elevation of Alanine Aminotransferase (ALT) and other liver function tests (AST, bilirubin, total and direct).
	
This has been observed in a variety of SARMs and was observed (minimal) in the 14-day and 13-week rat toxicity studies with administered GSK2881078.
 
One subject had elevations of Liver Function Tests (LFTs) in Phase 1a, but it was unclear if this was related to drug. Transient elevations in ALT without concomitant changes in bilirubin were observed in Phase 1b.
	
Monitoring of liver function tests will be in place at all clinic visits. This study will use follow up procedure that were used in Phase I of development of GSK2881078 for participants who have met liver stopping criteria, as detailed in Section 8.1.1 of this protocol.

Effects on reproductive organs/tissues:
 
Men – testes, epididymis, and prostate gland
 
Women – ovaries and uterus
	
These are recognized effects of SARM pharmacology and show recovery on discontinuation of dosing.
 
Test article-related organ weight and/or microscopic changes were observed in the gonads and other associated reproductive tissues in rat 14-day and 13-week toxicity studies administered GSK2881078. All test article-related microscopic findings were reversible after a 4- or 8- week off dose period. Test article-related effects were observed in male mating, fertility, gonadal function, and male-mediated development in a male rat fertility study.
 
In phase I studies, all male subjects dosed with
	
Males with PSA levels >4.0 ng/mL will be excluded.
 
Females will be post-menopausal.
 
Participants will be monitored at baseline, Day 28, Day 56, Day 89 and follow-up for changes in the following levels:
 
 • luteinizing hormone • follicle stimulating hormone • testosterone • free testosterone (calculated) • estradiol

Potential Risk of Clinical Significance	Summary of Data/Rationale for Risk	Mitigation Strategy
	GSK2881078 displayed reversible reductions in testosterone. No changes in PSA were recorded. Reversible reductions in sex hormone binding globulin were observed in both men and women. There were no clinically significant changes in FSH, LH, estradiol or progesterone.	
 • dihydrotestosterone • sex hormone binding globulin
Lowering of High-Density Lipoprotein (HDL) levels - A class effect of SARMs	All subjects dosed with GSK2881078 exhibited a reduction in HDL Cholesterol in Phase I studies. This reduction exhibited a dose response, with evidence of maximal pharmacology at a reduction of approximately 30-40% from baseline. This reduction was accompanied by a similar reduction proportionally in ApoA1. In all cases HDL Cholesterol returned to baseline on discontinuation of dosing.	Monitoring lipid profiles to confirm decreases seen on treatment, and whether lipid parameters return to baseline following discontinuation of study treatment. Lipid panels will be monitored at baseline, Day 56, Day 89 and at follow-up.
Bone effects	Minimal trabecular atrophy was observed in female rats at all doses in a 13- week toxicity study. This finding was not observed in male rats or dogs of either sex after 13 weeks of GSK2881078 administration.	
Bone turnover markers will be measured at baseline, Day 56, Day 89 and at follow-up. Bone biomarkers will include:
 
 • procollagen type I N propeptide (s-PINP) for formation • C-terminal telopeptide of type I collagen (s-CTX)
Anabolic abuse	Since this compound builds lean body mass, there is potential risk for anabolic abuse through illicit use of the drug by body builders.	Use of compound will be restricted to participants enrolled in study. Sites will have in place secure storage for compound supply. Sites to confirm restricted use of compound by enrolled participants at each study visit. Sites will be inspected for secure storage.

Potential Risk of Clinical Significance	Summary of Data/Rationale for Risk	Mitigation Strategy
Risks to women and foetal risk	Risks to women of possible androgenic effects from exposure to study compound by handling or by seminal exposure. In pregnant women, risk of exposure to compound during period of fetal reproductive differentiation.	Women who are not post-menopausal should avoid handling or ingestion of the study medication (capsules). Male participants should always use condom with female partners of childbearing potential. Sites to confirm compliance with guidelines by participants at each study visit.
Increase in absolute (not relative) heart weight	There is a theoretical risk that the anabolic effects of GSK2881078 are not only selective for striated skeletal muscle, and that there is an increase in cardiac muscle size. There are no pre-clinical or clinical data to support this risk.	Cardiac MRI will be carried out on a small subset of patients; the scan will be used to evaluate changes from baseline in cardiac size, structure and function in the treatment arm.
Study Procedures		
Risk of cardiac angina from incremental or endurance shuttle walk exercise tests	There is high incidence of cardiovascular comorbidity in COPD; undiagnosed disease may manifest during exercise tests	Physical exam, medical history and baseline ECGs will assess cardiovascular risk. Participants with a history of unstable angina will be excluded. Exercise tests will only be carried out under the supervision of suitably trained study personnel as detailed in the SRM.
Other		
None		

3.3.2. Benefit Assessment

Potential benefits of receiving GSK2881078 include gaining muscle mass, which may increase muscle strength and physical function, and may improve glycaemic control.

Participation in this study will contribute to the process of developing a new therapy in an area of unmet need, namely in people with COPD who suffer from muscle weakness.

Study participants will undergo medical evaluations and assessments associated with study procedures, which may be of benefit in identifying or monitoring COPD related features, e.g. physical examination, ECGs and laboratory tests can identify individuals at risk of cardiac comorbidity.

3.3.3. Overall Benefit: Risk Conclusion

Based upon review of available data from the FTIH study and the known and possible risks of therapy with GSK2881078, the potential therapeutic benefits of the SARM GSK2881078 for participants diagnosed with COPD and who suffer from muscle weakness warrant further study of the compound. Therefore, it is appropriate to proceed with this Phase II trial with medical supervision as outlined within this protocol.

4. OBJECTIVES AND ENDPOINTS

Objectives	Endpoints
Primary	

 Assess the safety and tolerability of approximately 13 weeks of dosing of GSK2881078 	
 Safety and tolerability of GSK2881078 as assessed by clinical monitoring of blood pressure (BP), heart rate, electrocardiogram (ECG) and laboratory safety data, as well as reporting of adverse events (AEs)

 Assess the effect of approximately 13 weeks of dosing of GSK2881078 on leg strength in older men and post-menopausal women with COPD and muscle weakness, participating in home exercise 	
 % change from baseline and change from baseline in maximum leg press strength following 1 repetition maximum (1- RM)
Secondary	

 Assess the effect of approximately 13 weeks of dosing of GSK2881078 on lean soft tissue mass 	
 Change from baseline in appendicular, and total lean mass as assessed by Dual-energy X-ray Absorptiometry (DXA)

Objectives	Endpoints

 Assess the effect of approximately 13 weeks of dosing of GSK2881078 on exercise capacity 	
 Change from baseline in total Short Physical Performance Battery (SPPB) score and times for chair rise and 4 m gait speed Change from baseline in Constant Work Rate (CWR) duration from endurance shuttle walking test Change from baseline in peak performance from incremental shuttle walking test

 Assess the effect of approximately 13 weeks of dosing of GSK2881078 on patient reported outcomes, levels of physical activity, activities of daily living and the patient perspective of efficacy 	
 Change from baseline in COPD Assessment Test (CAT) Change in PROactive endpoints (individual components and total score) Change in physical activity measures as assessed via an accelerometer Patient Global Impression of Change Patient Global Rating of Severity Change in St George Respiratory Questionnaire-COPD (SGRQ-c) total score and domains

 Assess the effect of approximately 13 weeks of dosing of GSK2881078 on respiratory function 	
 Change from baseline in forced expiratory volume in 1 second (FEV1) Change from baseline in Sniff nasal inspiratory pressure (SnIP)

 Characterise the population pharmacokinetic (PK) profile of approximately 13 weeks of dosing of GSK2881078 in older men and post-menopausal women with COPD and muscle weakness 	
 Model specific PK parameters of GSK2881078 (e.g., oral clearance, oral steady-state volume of distribution).

[figure not shown]
Objectives	Endpoints

 • Exploratory 	

 • Assess the safety of 13 weeks of dosing of GSK2881078 in older men and postmenopausal women in a subset of up to 15 male and 15 female participants with COPD via magnetic resonance imaging (MRI) 	
 • Changes from baseline in hepatic, prostate (males) and cardiac structure and function as assessed via MRI. Further exploratory analyses may include changes from baseline in size of inspiratory muscles and/ or other organs.

 • Conduct semi-structured exit interviews 	
 • Gain further insights into the participants' experience with study treatment and their participation in the trial.

 • Assess the effect of 13 weeks of dosing of GSK2881078 in older men and postmenopausal women on peripheral strength 	
 • Changes from baseline in handgrip strength • Potentially explore adherence to exercise program (daily physical activity and thrice-weekly strengthening exercises)

Additional exploratory analyses related to the primary and secondary endpoints will also be performed.

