10. STATISTICAL CONSIDERATIONS

Unblinded data will be reviewed in-stream by the study team. A Bayesian predictive approach using a non-informative prior will be used for the assessment of futility of the strength endpoint at an interim analysis. Although strength is the primary endpoint for the assessment of futility, the decision to continue or stop recruitment will be based on the totality of the data including strength, lean mass, functional endpoints, safety and tolerability.

After study completion, a Bayesian analysis using non-informative priors will be used to estimate posterior and posterior predictive distributions, as appropriate, for strength, lean mass and the functional endpoints to inform decision making. A multivariate Bayesian approach will be employed, data permitting

In addition, the effects of GSK2881078 relative to placebo on strength, lean mass and functional endpoints (i.e., incremental and endurance shuttle walk tests, and SPPB) will be evaluated using an estimation approach where point estimates and associated 90% confidence intervals (CI) will be constructed.

Descriptive statistics will be used to address safety, tolerability, PRO and PK objectives.

Data for male and female subjects will be analyzed separately. Depending on recruitment rates, analysis and reporting may be completed at different times for males and females.

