10.3.3. Other Analyses

Descriptive summaries and graphical displays will be prepared for measures of respiratory function (FEV1, SnIP).

The relationships between changes in lean mass or strength and other endpoints including but not limited to functional measures, PROs, and activity measures will be explored.

A multivariate Bayesian approach using non-informative priors will be employed, data permitting, to further explore the relationships between changes in strength and lean mass and the functional outcomes (ISWT, ESWT,) and to inform decision making. Details of the analysis will be described in the Reporting and Analysis Plan (RAP).

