### 7.2.2. Summary Measure

The adjusted mean treatment differences (GSK2881078 – Placebo) for the following endpoints will be presented:

- Change and % change from baseline in appendicular, and total lean mass as assessed by Dual-energy X-ray Absorptiometry (DXA) at Days 28, 56 and 90.
- Change from baseline in total Short Physical Performance Battery (SPPB) score, times for chair rise and 4 m gait speed at Days 28, 56 and 90.
- Change and % change from baseline in Constant Work Rate (CWR) duration from endurance shuttle walking test at Day 90.
- Change and % change from baseline in peak performance from incremental shuttle walking test at Day 90.
- Change from baseline in PROactive endpoints at Days 56 and 90. (individual components and total score).
- Change from baseline in COPD Assessment Test (CAT) score at Days 56 and 90.
- Change from baseline in St George Respiratory Questionnaire (SGRQ) total score and domain scores derived from SGRQ-c raw scores at Days 90.

The responder analysis between GSK2881078 and Placebo (GSK2881078/ Placebo) for the following endpoints will be explored

- Odds ratio between treatment groups for the COPD Assessment Test (CAT) responder at Days 56 and 90.
- Odds ratio between treatment groups for the St George Respiratory Questionnaire (SGRQ) responder defined by the total score derived from SGRQ-c raw scores at Days 90.

The descriptive summaries will be reported for the following endpoints

- Change from baseline in forced expiratory volume in 1 second (FEV1).

- Frequency and percentages of Patient Global Impression of Change (PGIC) responses.
- Frequency and percentages of Patient Global Rating of Severity (PGRS) responses.
- Change from baseline in Sniff nasal inspiratory pressure (SnIP).
- Change in physical activity measures as assessed via an accelerometer.

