**7.2.4.1. Statistical Methodology Specification**

Secondary Efficacy Endpoint / Variables – Multiple Post-baseline Visit

 
• Change and % change from baseline in appendicular, and total lean mass as assessed by Dual-energy X-ray Absorptiometry (DXA) at Days 28, 56 and 90.
 
• Change from baseline in total Short Physical Performance Battery (SPPB) score, **time for repeated chair rise and 4 m gait speed at Days 28, 56 and 90.
 
• Change from baseline (Day 1) in *PROactive endpoints (individual components (difficulty and amount score) and **total score) at Days 56 and 90.
 
• Change from baseline in COPD Assessment Test (CAT) score at Days 56 and 90.
 
 
*A physical activity monitor will be worn for 7 days after the Day -9 visit (Day 1), for 7 days after the Day 56 visit (Day 56), and for 7 days following the day 80 visit (Day 90).
 
**Bayesian analysis will be performed only for the endpoints change from baseline of PROactive total scores and change from baseline in the time for repeated chair rise. The posterior probability of treatment difference greater than 3 points and less than 6 points for PROactive total scores and greater than 1.3 seconds and less than 1.7 seconds for time for repeated chair rise will be estimated for each visit separately by gender.

Model Specification

 
• Treatment difference (GSK2881078 – placebo) at each visit on change from baseline or percentage change from baseline (as appropriate) will be analysed using mixed models repeated measures (MMRM) models as what was described for the primary efficacy endpoint in Section 7.1.4.1. The analyses will be based on the analysis population for all endpoints additionally the endpoints PROactive and SPPB will be analysed for per-protocol population as well.
 
• If there are any departures from the distributional assumptions for change or percentage change from baseline, the change of log-transformed data at post- baseline from log baseline will be the response variable, adjusted for treatment, log-transformed baseline value, day and
 

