**Summary Results Presentation**

Baseline, each postbaseline visit and change from baseline, will be descriptively summarized by treatment group for endpoints: weekly average steps, vector magnitude unit/wear time and moderate/vigorous activity duration measures via an accelerometer. The number of subjects with the eligible days i.e. wear duration more than 8 hours for at least 4 days, the average eligible days for those subjects and average wear duration (minutes) during the eligible days will be summarized.

Baseline, each postbaseline visit and change from baseline, will be descriptively summarized by treatment group for original FEV1 (L) and percentage predicted FEV1 and maximum SnIP.

In addition, a box plot will be prepared for the change from baseline for FEV1 and SnIP at the post-baseline visits.

For the categorical endpoints, PGRS and PGIC, the count and percentage will be summarized by category and treatment for each visit separately by gender.

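### FEV1, SnIP and accelerometer activity are secondary endpoints under objectives to assess the drug's effect, but no adjusted treatment difference or 90% CI is planned for them

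*Protocol*

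**What the plan says.** **Objectives.** Protocol section 4, repeated in SAP 2.2, lists a secondary objective to "Assess the effect of approximately 13 weeks of dosing of GSK2881078 on respiratory function". Its two endpoints are change from baseline in FEV1 and in SnIP. A second objective, covering patient-reported outcomes and levels of physical activity, includes "Change in physical activity measures as assessed via an accelerometer" alongside CAT, PROactive, SGRQ-c, PGIC and PGRS.

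**Planned analysis in the protocol.** Section 10 says that strength, lean mass and the functional endpoints will be "evaluated using an estimation approach where point estimates and associated 90% confidence intervals (CI) will be constructed". FEV1, SnIP and the accelerometer measures are not named there. Section 10.3.3 plans summaries and graphs for FEV1 and SnIP.

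**Planned analysis in the SAP.** Section 7.2.2 has two relevant lists.
- Under "The adjusted mean treatment differences (GSK2881078 – Placebo) for the following endpoints will be presented" it names lean mass, SPPB with chair rise and gait, CWR duration, incremental shuttle walk, PROactive, CAT and SGRQ.
- Under "The descriptive summaries will be reported for the following endpoints" it names FEV1, SnIP, accelerometer measures, PGIC and PGRS.

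Section 7.2.4.1 adds that results "will be descriptively summarized by treatment group for original FEV1 (L) and percentage predicted FEV1 and maximum SnIP", and treats weekly steps, VMU per wear time and moderate/vigorous minutes in the same way. Tables 2.40, 2.43 and 2.44 use shell EFF_T3, which shows n, mean, SD, median, minimum and maximum per arm. Figures 2.7 and 2.8 are box plots, and Figure 2.9 is a descriptive plot of mean change in daily steps.

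**The concern.** In a placebo-controlled trial, the effect of a drug on a continuous outcome is a difference between arms. For the respiratory objective no planned output shows that difference or its uncertainty, and the objective has no other endpoint. SnIP matters more because SAP Table 1 drops the possible MRI analysis of inspiratory-muscle size, as no data were collected.

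The missing-data pattern makes raw visit means less attractive here. Under protocol sections 8.1 and 8.2, a participant who has a severe exacerbation, or one treated with oral steroids, stops study treatment and afterwards has only follow-up safety assessments. The schedule has no spirometry or SnIP at follow-up, and section 10.2 rules out imputation. Day 90 FEV1 will therefore tend to be missing in participants who had such exacerbations, which is plausibly related to lung function. An observed-case Day 90 mean leaves those participants out. An MMRM uses their Day 56 values, under a missing-at-random assumption.

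**Working it through.** **1. Same structure, different analysis.**

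| Endpoint | Baseline | On-treatment times | Planned analysis |
|---|---|---|---|
| CAT | Day 1 | Days 56, 90 | MMRM, difference, 90% CI |
| PROactive | 7 days after Day -9 | weeks after Days 56 and 80 | MMRM, difference, 90% CI |
| FEV1, SnIP | latest pre-dose | Days 56, 90 | per-arm description |
| Accelerometer | 7 days after Day -9 | weeks after Days 56 and 80 | per-arm description |

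The CAT entry in SAP 7.2.4.1 is "Change from baseline in COPD Assessment Test (CAT) score at Days 56 and 90". Protocol section 10 had assigned descriptive statistics to the PRO objectives, so the SAP has already moved CAT, PROactive and SGRQ from description to a model.

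**2. The protocol's own precision figures.** Half-width of the 90% CI = t(0.95, 2n − 2) × SD × √(2/n). For strength (protocol 10.1.1, SD 10.9):
- n = 20 per arm gives 5.81, against 5.8 stated.
- n = 10 per arm gives 8.45, against 8.45 stated.

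The same formula matches the stated values for lean mass, ISWT and ESWT.

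**3. What a reader could derive for the omitted endpoints.** The documents give no SD for them, so work in SD units of the change. At n = 20 per arm: t(0.95, 38) × √(2/20) = 0.533 SD. At n = 25 the figure is 0.474 SD. As an illustration only, an assumed FEV1 change SD of 0.10 to 0.30 L gives 0.05 to 0.16 L at n = 20.

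**4. What the model would add.** Assumptions:
- 25 randomised per arm (protocol 5.2).
- 10% lost by Day 56 and 20% by Day 90. The protocol gives only the overall figure of about 20%.
- Equal variances and a common correlation ρ between visits.

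The effect of baseline adjustment alone has a closed form. The variance of a raw change is 2(1 − ρ). After adjustment for baseline it is 1 − ρ². The SE ratio is therefore √((1 + ρ)/2).

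| ρ | Baseline adjustment alone, formula | Simulated MMRM/raw SE ratio | Reduction in SE |
|---|---|---|---|
| 0.5 | 0.87 | 0.88 | 12% |
| 0.7 | 0.92 | 0.93 | 7% |
| 0.9 | 0.97 | 0.97 | 3% |

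The formula accounts for almost all of the simulated gain, so most of the precision comes from baseline adjustment. With these loss rates the Day 56 data add little precision. Their value lies in how participants lost between Day 56 and Day 90 are handled.

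**5. Resulting interval.** At 20 per arm with one more model parameter, t(0.95, 37) × √(2/20) = 0.534 SD. Multiplying by the formula ratios gives 0.534 × 0.866 = 0.46 SD at ρ = 0.5 and 0.534 × 0.975 = 0.52 SD at ρ = 0.9.

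**6. Multiplicity cost.** 5 measures × 2 visits × 2 sexes = 20 intervals. At the 90% level, 20 × 0.10 = 2 would be expected to exclude zero if there were no effect.

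**The case against.** The strongest defence is that the choice is deliberate and consistent. Protocol 10.3.3 planned description for FEV1 and SnIP, and the SAP keeps to it. The trial is a proof-of-concept study sized on strength, and none of these measures is among the decision-making endpoints named in SAP 7.2.3. An objective to assess an effect does not always lead to a modelled interval in these documents. Handgrip strength has such an objective and is only described; so are PGIC and PGRS, and safety is summarised without formal comparison. All of this stands. It rules out reading the point as a contradiction between protocol and SAP, and it lowers the priority.

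Two stronger readings are tempting.
- A reader might infer that the trial cannot answer its respiratory objective. That goes too far: shell EFF_T3 sets the randomised arms side by side within sex, and its n, mean and SD give an unadjusted difference and interval.
- A reader might infer that Day 56 data are ignored. They are not: every post-baseline visit is summarised. What is lost is their contribution to the Day 90 estimate.

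For activity, the gap is partly covered. Steps per day and VMU per minute enter the PROactive amount score, which gets an MMRM difference and 90% CI. They enter only as categories combined with diary items, so the accelerometer measures themselves still have no estimate.

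The defence does not supply a reason for treating continuous measures with the same visit structure as CAT and PROactive differently.

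**Conclusion.** The point holds as a mismatch between objective and analysis. FEV1, SnIP and the accelerometer measures have no planned adjusted difference or 90% CI, although the SAP already contains a model that fits their structure. The gap is clearest for the respiratory objective, which has no other endpoint.

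The loss is moderate. An unadjusted interval of about ±0.53 SD of the change can be derived by hand at 20 per arm. The MMRM would reduce the standard error by about 3% to 12%. That range rests on assumed correlations of 0.5 to 0.9 and an assumed 10%/20% loss pattern, none of which the documents give for these endpoints. No bias has been shown. The missing-data argument is one of plausibility, and the MMRM answers it only if data are missing at random. PGIC and PGRS are also descriptive only, but they are categorical and do not suit this model.

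**What to change.** In SAP 7.2.2 and 7.2.4.1, move FEV1 (L), maximum SnIP and the weekly-average accelerometer measures (steps, VMU per wear time, moderate/vigorous minutes) from *Descriptive Summary* to *Multiple Post-baseline Visit*.

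- Fit the MMRM of SAP 7.1.4.1 separately by sex, with treatment, day, treatment × day and baseline.
- Report adjusted means and the GSK2881078 minus placebo difference with 90% CI at Day 56 and at Day 90 (Day 80 week for the accelerometer), labelled as supportive estimates.
- Apply the SAP's existing log-transform rule. Logs cannot be taken of zeros, which moderate/vigorous minutes may contain, so state in advance how that measure will be handled.
- Use one label for the last monitor week. SAP 7.2.4.1 calls it Day 90 for PROactive and Day 80 for the accelerometer measures.
- Keep Tables 2.40, 2.43 and 2.44 and Figures 2.7 to 2.9, and add a line to SAP Table 1 recording the change.

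The cost is SAP wording and a few tables from a model that is already specified. No new data are needed. The downside is about 20 more intervals without multiplicity adjustment, of which about two would exclude zero by chance. SAP 5.5 already accepts unadjusted secondary analyses, and the supportive label guards against over-reading. If the sponsor prefers description only, the objective wording should be changed to match.
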